### **2. Treatment**

Patients can receive ongoing treatment every 4 weeks or as close to this interval as permitted due to practical or logistic considerations until death or withdrawal, unless such therapy is contraindicated, the patient does not wish to continue or the study is terminated by the Sponsor. At no point should the elapsed period between IMM-101 doses be less than 14 days. The Study Flow Chart of Assessments is provided as Appendix 1.

Patients may choose to withdraw from the study at any time and for any reason. IMM-101 should be stopped or the dosing regimen reduced if felt to be necessary by the Investigator and/or patient (e.g., intolerable injection site reactions). In the event of an injection site reaction of Grade 3 and above, and/or if significant ulceration, tenderness or lymphadenopathy is observed, at the discretion of the Investigator, patients may be administered a half dose of the study drug (i.e., a single 0.05 mL intradermal injection of IMM-101) or the timing of the injection may be delayed. If the dosing interval is increased, the patient should still attend the study site for safety assessments preferably every 3 months but, if this is not possible, every 6 months at a minimum. In addition, if the patient does not attend the clinic for a study visit within a calendar month, the clinic will telephone the patient to enquire about injection site reactions, adverse events, concomitant medications and any other concerns. Details of the call will be recorded in the patient notes with appropriate information on adverse events and concomitant medications also being recorded in the CRF. The blood sample for exploratory analysis should continue to be taken every 6 months.

Any change in the dose of study drug administered or the frequency of dose administration should be recorded in the patient's case report form (CRF). In the case of withdrawal, separate consent will be sought to allow the continued collection on patient status.

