4. PLANNED ANALYSES

At the time of final analysis for the study, descriptive summaries of the results of the study will be provided along with data listings of the final study database. Summary statistics or frequency tables will be provided, where appropriate.

Section 9 provides details of the descriptive statistics and TFL shells are included in Section 13.

No formal statistical analyses of the results are anticipated and hence no statistical inferences will be made.

Planned analyses as detailed in the protocol are as follows:

The evaluation of safety and tolerability will be summarised using the Safety population and will be based on local and systemic toxicities (including injection site tolerability) which will be presented over the treatment period in standard frequency tables, overall and by number, degree and type. Adverse Events will

be presented descriptively to include related adverse events, serious adverse events (SAEs), and adverse events leading to withdrawal or death. The frequency and severity of injection site reactions, and all other safety parameters will be summarised.

All patients will have received IMM-101 in the context of both the Phase 1 study and, for the majority, on a Named Patient basis; therefore all AEs in this long term follow up study will be regarded as treatment emergent.

Efficacy will be presented using the Safety population and will be assessed through documenting the long-term clinical course of the patients previously enrolled in Study IMM-101-001 in terms of OS. Reduction in metastatic disease will be listed only.

Variables for the exploratory endpoints will be analysed and reported separately to the main efficacy and safety endpoints of the study.

The protocol specified that OS will be presented from enrolment into this study, in addition to time from initial diagnosis and enrolment into study IMM-101-001. Time zero for the OS analysis in this study (IMM-101-008) will be based on the date of Day 0 in this study and analysis of OS taking into account time from initial diagnosis and first dosing day in Study IMM-101-001 will not be included in this SAP as not all patients completing the FIH study entered the LTF study.

In addition to the above planned presentations, non-serious adverse events in LTF study patients will be tabulated and treatment-related treatment emergent AEs will also be presented combining data in these patients, from both the FIH and LTF studies.

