7. GENERAL CONSIDERATIONS FOR DATA ANALYSES

In general, continuous data will be summarised using mean, standard deviation, minimum, median and maximum. The minimum and maximum will be recorded to the same number of significant figures as the

original data, whilst mean and median will be presented to 1 significant figure more than the original data, and standard deviation 2 significant figures more than the original data.

In summaries of categorical data, frequency counts and percentages will be used. Generally, percent will be displayed to one decimal place.

The time to event variable OS will be analysed using standard Kaplan-Meier techniques. The Kaplan Meier curve will be plotted and median (50%), 25% and 75% survival estimates reported with the corresponding 95% confidence intervals (CIs).

All analyses will be performed using SAS v 9.4 (or higher).

All tables, figures and listings (TFLs) will include titles, headers or footnotes which identify:-

- The analysis set on which the presentation is based.
- A description or title for the presentation (where combined data is presented from the FIH study and the LTF study, this will be indicated).
- The date and time the output was produced.
- A reference to the name and location of the file used to produce the output and the source of the data used (which may be a SAS dataset or another TFL).
- Reference to the analysis stage of the study data e.g. Final Analysis.

Listings which present data using repeating rows for a patient and/or visit will be presented in chronological date order (where applicable) with the repeating header information presented on the first new record for each repeating combination only, to facilitate readability.

All assessment data will be reported with the visit at which it was recorded, whether or not the visit falls inside the relevant window or not.

Tables and figures will be coded from Analysis Data Model (ADaM) format datasets. Listings will be coded from Study Data Tabulation Model (SDTM) datasets.

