9.3 Study Treatment, Exposure and Safety Outputs

An on-study administration table (Table 7) will show the number and percentage of patients who receive study drug and whether full dose or reduced dose was administered, summarised by visit. In these

presentations, the denominator for the calculation of percentages at each visit will be based on the number of patients available at each visit who provide a response.

A line graph for each patient will be plotted to visually display any variation in doses of IMM-101 (in mg) by time, during the LTF study. This will be presented in the form of a panel plot (Figure 1a) on standard axes for each patient. Each dose will be marked by an 'X' on the plot. In addition, a panel plot (Figure 1b) will be presented including all IMM-101 doses received from the first dose in the FIH study, to the last dose in the LTF study, inclusive including those taken whilst the patient was being treated in the NPP, in a similar manner.

Exposure, to include the time on LTF study in years, overall LTF study drug exposure (months) and total no. doses on study, will be summarised in Table 9a.

Overall exposure to IMM-101 from first dose in the FIH study to last dose in the LTF study inclusive will be summarised in Table 9b.

Summaries of adverse events will include the number of adverse events and the proportion of patients experiencing at least one adverse event. If an individual patient has more than one AE at a given level of classification the patient will be counted only once at the given level of classification but each event will be counted within the number of events associated with that level of classification.

All patients will have received IMM-101 in the context of both the Phase 1 study IMM-101-001, and, for the majority, during the NPP; therefore all AEs in this long-term follow-up study will be regarded as treatment-emergent.

Table 10a includes the incidence and frequency of all TEAEs, treatment emergent treatment-related AEs, treatment emergent SAEs, Serious treatment-related TEAEs, TEAEs resulting in withdrawal or death and AEs of NCI CTCAE Grade ≥ 3 .

Frequency summaries of treatment emergent adverse events by SOC and PT using MedDRA v 18.0 (or higher) will be included overall (Table 10b) and repeated to capture:-

- Treatment emergent adverse events of NCI Grade ≥ 3 (Table 10c)

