- Treatment emergent, IMM-101-related, adverse events: AEs that are definitely, probably or possibly related to study drug or with an unknown relationship (Table 10d)
- Treatment emergent, SAEs (Table 10e)
- Treatment emergent adverse events leading to withdrawal or death (Table 10f).
- Treatment emergent non-serious adverse events (Table 10g).

Additionally, long term safety will be evaluated by combining treatment related adverse event experience in the FIH study through to the end of the LTF study by summarising treatment emergent treatment-related adverse events (IMM-101-001 and IMM-101-008 Combined) (Table 10h).

Where it is not applicable to grade an AE using NCI CTCAE grade, it will be excluded from the summary of NCI Grade 3 and above AEs. Any AEs with missing grades, however, will be included, based on a worst-case approach.

On-study injection site reactions are summarised over the treatment period by visit in Table 11.

Urine Pregnancy Test Results and blood samples for immunological markers will be listed but not summarised.

All safety data will be listed.

Any comments recorded as free text in the CRF will be listed.

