Total Number of treatment-related treatment emergent adverse events	xx
System Organ Class	n (xx.x) m
Preferred Term	n (xx.x) m

Note: n = number of patients with an AE; m = number of AEs.

Hence if a patient has multiple AEs only one occurrence per person will contribute to 'n', but all occurrences will be counted under 'm' as this is the total number of events recorded.

Note: Preferred Term and System Organ Class are coded using MedDRA version 18.1.

Note: Percent is based on the total number of patients in the Safety Population.

Note: Treatment emergent AEs are all those reported at/after first IMM-101 dosing in study IMM-101-001. Related AEs are defined as AEs that are definitely, probably or possibly related to study drug or with an unknown relationship.

Code: S:\Services\Immodulon\IMM-101-008\Analysis\Development\Code\ Table10h.sas ddmmmyy:hh:mm:ss

Data: S:\Services\Immodulon\IMM-101-008\xxxxx.sas7bdat

Data: S:\Services\Immodulon\IMM-101-001\xxxxx.sas7bdat

Note to programmer: Please update data footnote with appropriate file directory.**Note to Programmer:** Order by most common (by incidence) SOC and PT within SOC.

CONFIDENTIAL

Exploristics Limited

Identifier: EXP12002

Clinical Study Identifier: IMM-101-008

Final Analysis

Protocol: IMM-101-008

Analysis Population: Safety Population

Page x of y

Table 11
On-Study Injection Site Reaction(s)

	Visit 1 N = xx (%)	Visit 2 N = xx (%)	Visit N N = xx (%)
Is the injection site reaction from previous IMM-101 dose(s) visible?	N	N	N
Yes	xx (xx.x)	xx (xx.x)	xx (xx.x)
No	xx (xx.x)	xx (xx.x)	xx (xx.x)
If visible, are daily activities affected?	N	N	N
Not at all	xx (xx.x)	xx (xx.x)	xx (xx.x)
Slightly	xx (xx.x)	xx (xx.x)	xx (xx.x)
Moderately	xx (xx.x)	xx (xx.x)	xx (xx.x)
Quite badly	xx (xx.x)	xx (xx.x)	xx (xx.x)
Intolerably	xx (xx.x)	xx (xx.x)	xx (xx.x)
Worsening with repeated doses of IMM-101?	N	N	N
Yes	xx (xx.x)	xx (xx.x)	xx (xx.x)
No	xx (xx.x)	xx (xx.x)	xx (xx.x)
Not Sure	xx (xx.x)	xx (xx.x)	xx (xx.x)
Wound care required?	N	N	N
Yes	xx (xx.x)	xx (xx.x)	xx (xx.x)
No	xx (xx.x)	xx (xx.x)	xx (xx.x)

Note: Percent are based on the number of patients available at each visit who provided a response.

Code: S:\Services\Immodulon\IMM-101-008\Analysis\Development\Code\Table11.sas ddmmmyy:hh:mm:ss

Data: S:\Services\Immodulon\IMM-101-008\xxxxx.sas7bdat

Note to programmer: Please update data footnote with appropriate file directory.

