Clinical Study Identifier: IMM-101-008

Final Analysis

Protocol: IMM-101-008

Analysis Population: Safety Population

Page x of y

Listing 15
Study Visits and Visit Checklists

Unique Patient ID	Visit Name/Number	Visit Date (DD-MM-YYYY)	Number of weeks elapsed since last visit (where applicable)	Checklist Item	Completed (Y/N)
xxxxx	xxxxx	DD-MM-YYYY	xx	xxxxx	xx
xxxxx	xxxxx	DD-MM-YYYY	xx	xxxxx	xx
xxxxx	xxxxx	DD-MM-YYYY	xx	xxxxx	xx
xxxxx	xxxxx	DD-MM-YYYY	xx	xxxxx	xx
xxxxx	xxxxx	DD-MM-YYYY	xx	xxxxx	xx
xxxxx	xxxxx	DD-MM-YYYY	xx	xxxxx	xx
xxxxx	xxxxx	DD-MM-YYYY	xx	xxxxx	xx
xxxxx	xxxxx	DD-MM-YYYY	xx	xxxxx	xx

Code: S:\Services\Immodulon\IMM-101-008\Analysis\Development\Code\Listing15.sas ddmmmyy:hh:mm:ss

Data: S:\Services\Immodulon\IMM-101-008\xxxx.sas7bdat

Note to programmer: Include Date of Consent for patient transfer to Site 2, date of first visit at Site 2 and nominal visit number according to CRF entries, in chronological order in the listing (see Immodulon file note FN47).

Note to programmer: Please update data footnote with appropriate file directory.

Note to programmer: Visit Name/Number should be one of Screening, Day 0 or Routine Visit xx.

Note to programmer: All visits should be listed. Checklist items text to be stated in full. If text too long, add a key on separate listing 15a or similar.

CONFIDENTIAL**Exploristics Limited**

Identifier: EXP12002

Clinical Study Identifier: IMM-101-008

Final Analysis

Protocol: IMM-101-008

Analysis Population: Safety Population

Page x of y

Listing 16
Blood Sample for Immunological Markers

Unique Patient ID	Visit Name/ Number	Visit Date (DD-MM-YYYY)	Blood Sample Taken? (Y/N)	Volume (mL)
xxxxxx	xxxxxx	DD-MM-YYYY	xx	xx.x
xxxxxx	xxxxxx	DD-MM-YYYY	xx	xx.x
xxxxxx	xxxxxx	DD-MM-YYYY	xx	xx.x
xxxxxx	xxxxxx	DD-MM-YYYY	xx	xx.x
xxxxxx	xxxxxx	DD-MM-YYYY	xx	xx.x
xxxxxx	xxxxxx	DD-MM-YYYY	xx	xx.x
xxxxxx	xxxxxx	DD-MM-YYYY	xx	xx.x
xxxxxx	xxxxxx	DD-MM-YYYY	xx	xx.x

Code: S:\Services\Immodulon\IMM-101-008\Analysis\Development\Code\Listing16.sas ddmmmyy:hh:mm:ss

Data: S:\Services\Immodulon\IMM-101-008\xxxxxx.sas7bdat

Note to programmer: Please update data footnote with appropriate file directory.**Note to programmer:** Visit Name/Number should be one of Screening, Day 0 or Routine Visit xx.

CONFIDENTIAL**Exploristics Limited**

Identifier: EXP12002

Clinical Study Identifier: IMM-101-008

Final Analysis

Protocol: IMM-101-008

Analysis Population: Safety Population

Page x of y

Listing 17

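### Table 11 summarises injection site reactions by visit number, which is neither time nor dose count and may depend on the reactions themselves; time since Day 0 would be a better axis

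*SAP*

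**What the plan says.** SAP 9.3: "On-study injection site reactions are summarised over the treatment period by visit in Table 11". The shell in SAP 13.2 has columns Visit 1, Visit 2 and so on to Visit N. Table 7 is built the same way, showing "whether full dose or reduced dose was administered, summarised by visit". Its percentages are "based on the number of patients available at each visit who provide a response", and the footnote to the Table 11 shell applies the same rule. SAP 7 rules out re-windowing: "All assessment data will be reported with the visit at which it was recorded, whether or not the visit falls inside the relevant window". The listings label each visit as Screening, Day 0 or a routine visit number.

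Spacing between visits is flexible. Protocol 5.2 sets a nominal 4-week dosing interval with a 14-day minimum. If the dosing interval is increased, safety attendance should be "preferably every 3 months but, if this is not possible, every 6 months at a minimum". A poor local reaction is a named reason to prolong the interval (Protocol 3.5, 5.2, 7.5 and 9.1.3.1). The same sections allow a reduced dose instead, and intervals may also vary for practical reasons.

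Reactions are assessed before each injection (Protocol 9.1.3.1 and 9.2) and become adverse events only if the Investigator thinks it appropriate. Listings 10 and 13 carry visit and last-dose dates. Listing 15 has visit dates and a column headed "Number of weeks elapsed since last visit (where applicable"). Figures 1a and 1b plot dose, not reactions, against time.

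**The concern.** Protocol 3.4 names one potential risk of continued treatment: that site reactions may increase as doses accumulate. Table 11 is the only planned summary of the on-study reaction assessments, so it is where a reader will look for that trend, reading across the columns.

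The column index does not suit that reading. With variable spacing, a visit number fixes neither time on drug nor number of doses; Table 7 has its own row for visits without a dose. The index may also depend on the outcome. A patient whose interval is lengthened because of a reaction accrues visits more slowly and may never reach the later columns while still on study. Those columns could then look better because of who is left in them.

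There is a second, separate distortion. Reactions are inspected just before the next dose, so a longer gap gives the last site more time to heal and can lower the recorded reaction even with the same patients present.

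**Working it through.** There is no sample size, power or significance level to reproduce; Protocol 10.2 and 10.3 are both marked not applicable. The check has three parts.

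**1. What a visit number means.** Inputs: the latest possible follow-up, from the date of protocol version 1.0 (15 September 2011, Protocol Appendix 4) to December 2018 (footnote to SAP Listing 1), taken as 1 December. That is 2,634 days, or 2,634/365.25 = 7.2 years. No Day 0 dates are given, so this is an upper limit. Sequential numbering is assumed. Visits including Day 0 = floor(2,634/interval) + 1; routine visit 24 falls at 24 × interval/365.25.

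| Constant interval | Visits possible | Time of visit 24 |
|---|---|---|
| 14 days (minimum between doses) | 189 | 0.9 years |
| 28 days (nominal) | 95 | 1.8 years |
| 91.3 days (3-monthly attendance) | 29 | 6.0 years |
| 182.6 days (6-monthly attendance) | 15 | 12.0 years, never reached |

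**2. Direction of a possible artefact.** This is an illustrative simulation of 400 replicates with 10 patients and no true change with repeated dosing. Assumed, not from the documents: 4 patients have a 60% chance of a bad reaction at each visit and 6 have 10%, so the true rate is (4 × 60% + 6 × 10%)/10 = 30%. Visits are 28 days apart unless a bad reaction lengthens the next gap. Each cell gives the by-visit bad-reaction rate, then the share of patients present who are poor tolerators (40% at entry).

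| Scenario | Visit 24 | Visit 40 | Visit 60 |
|---|---|---|---|
| Every bad reaction lengthens the gap to 3 months | 30%, 40% | 21%, 22% | 9%, 0% |
| Every bad reaction lengthens it to 6 months | 17%, 13% | 10%, 0% | 11%, 0% |
| Half lengthen to 3 months | 31%, 40% | 31%, 40% | 17%, 15% |
| None lengthen | 30%, 40% | 30%, 40% | 30%, 40% |
| 3 months, plus unrelated dropout (mean 4 years) | 24%, 29% | 16%, 12% | 11%, 0% |

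With dropout, the mean number present is 4.5 at visit 24 and 2.7 at visit 40.

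The 3-month scenario was also summarised by year since Day 0, averaging each patient's own proportion of bad assessments. That gave 32–33% in each of the seven full years: flat, though slightly above 30%, because a bad assessment followed by a long gap leaves fewer others in that year. With 6-month gaps it gave 34% in year 1 and about 36–37% in years 2 to 7.

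If a recorded reaction is assumed half as likely after a long gap, the by-visit rate drops from 30% to 23% at the first routine visit with no change in who is present. That is the healing effect alone.

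**3. Choice of summary within an interval.** Taking each patient's worst response would not be safe. At a constant 20% risk per assessment, the chance of at least one reaction in 6 months is 1 − 0.8⁶ = 74% with six visits, 1 − 0.8² = 36% with two, and 20% with one. A patient moved to longer gaps would appear to improve.

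**The case against.** Several points on the other side have force. A half dose is offered alongside a longer interval, and Protocol 7.5 favours continuing, at a lower dose if need be, over withholding. If half doses were the usual response, the columns would not be selected by tolerance, as the scenario without lengthening shows. Table 11 also contains an item that asks the patient's own history, "Worsening with repeated doses of IMM-101", and its column headings show N. Reactions reported as adverse events enter Tables 10a to 10h, which are not by visit. The cohort is small: 18 − 3 − 1 − 2 = 12 still on treatment in August 2011 (Protocol 4.2), and the 2×5 panel in SAP Figure 1a suggests about 10, so a reader could follow each patient through Listing 13. SAP 4 adds: "No formal statistical analyses of the results are anticipated and hence no statistical inferences will be made".

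These points limit the consequence without curing the axis. The worsening item is still tabulated by visit number, adverse event reporting of reactions is discretionary, and a descriptive table should not need rebuilding from listings.

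Stronger readings are tempting but not supported:

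- A reader might infer that late columns hold mainly good tolerators, or that any trend is distorted. The documents do not say how intervals were actually managed. Death, withdrawal, logistics, entry date and the December 2018 stop also decide who reaches late columns, and with 3-month lengthening and no dropout the simulated columns were intact at visit 24.
- A reader might infer that about 70% of columns are closed to slower attenders ((95 − 29)/95 = 69%). That needs a patient seen 3-monthly from Day 0 and follow-up at its upper limit.
- Six months limits safety attendance; no maximum dosing interval is stated.
- Sequential numbering is the natural reading but is not stated. A programmer note to Listing 15 refers to a nominal visit number, and the flow chart uses nominal weeks. If the numbers follow nominal weeks, the concern shrinks.
- Table 7 measures no reactions, and Figures 1a and 1b already give dose by time.

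**Conclusion.** The concern holds in a limited form. Table 11 uses an index that is neither time nor dose count and that the plan allows to depend on the reactions being measured. If visits are numbered in sequence, one column can mix patients years apart in exposure, and later columns may under-represent those whose intervals were lengthened for poor tolerability. An apparent decline with repeated dosing could then be an artefact of the layout and of longer healing times.

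The size cannot be determined from the documents. In the simulation it ranges from nothing, when no interval is lengthened, to a fall from 31% at Day 0 to 9% at visit 60 when every bad reaction leads to a 3-month gap. The reaction rates, patient split and dropout are assumptions, so only the direction should be relied on. This is a presentation weakness in a small descriptive study, not an invalid test, but it bears on the named safety risk and is worth correcting before the tables are run.

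**What to change.** 1. State in the SAP how CRF visits are numbered: in sequence, or by nominal week.
2. Summarise Table 11 by time since Day 0, for example in 6- or 12-month intervals from visit dates. Within each interval give each patient equal weight, using the proportion of that patient's assessments in each response category rather than the worst response.
3. Use patients assessed in the interval as the denominator, and show the numbers on study, assessed and not assessed. Dividing by everyone on study would count unassessed patients as unaffected.
4. Show days since last dose for each interval, so that longer healing time is visible.
5. Optionally add a display by cumulative dose number, with n per column and a note that patients on longer intervals drop out of the later columns. It should not replace the time display.
6. Table 7 needs at most the same time axis. Keep visit-level data in Listings 10 and 13.

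Cost: a little reprogramming from dates already in Listings 10, 13 and 15, and less visit-level detail in the table. The proportions will rest on few assessments for patients with long gaps, so their level may sit slightly high, as in the simulation; a footnote should say so.
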